**Table 7 Hematological Monitoring Criteria**

Platelet Count Value	Monitoring
$75 \times 10^9 / \text{L} \leq \text{platelets} < 100 \times 10^9 / \text{L}$	Monitor weekly until $\geq 100 \times 10^9 / \text{L}$
$50 \times 10^9 / \text{L} \leq \text{platelets} < 75 \times 10^9 / \text{L}$	Assess anti-platelet antibodies Monitor every 2 to 3 days until 3 successive measurements $\geq 75 \times 10^9 / \text{L}$ , then weekly until $\geq 100 \times 10^9 / \text{L}$
$< 50 \times 10^9 / \text{L}$	Assess anti-platelet antibodies Monitor daily until $> 25 \times 10^9 / \text{L}$ , then every 2 to 3 days until 3 successive measurements $\geq 75 \times 10^9 / \text{L}$ , then weekly until $\geq 100 \times 10^9 / \text{L}$

### 7.1.3. Drug induced kidney injury (renal) monitoring

If any of the following are observed, results should be confirmed (with a new blood sample), and if confirmed, further evaluation for alternative causes should be pursued in consultation with the Medical Monitor:

- Persistent uACR  $> 0.3 \text{ mg/mg}$  ( $> 300 \text{ mg/g}$ )
- Blood in urinalysis  $> 5$  red blood cells per high power field confirmed by urine microscopy (unless there is a known cause [e.g., females during menstruation])
- Gradual and consistent reductions of eGFR compared with baseline.

Following confirmation of the criteria above, if underlying cause other than drug-induced renal injury is not confirmed, further evaluation may include but not be limited to a 24 hour urine analysis, consultation with a nephrology specialist, renal ultrasound, urine microscopy, serum urea and creatinine, platelet count, urgent serum vasculitis screen (including ANCA, ANA, dsDNA, Rheumatoid Factor, cryoglobulins), SPEP/UPEP, and complement panel (C3, C4, C5a and Bb). Further evaluation and actions should be determined by the investigator in consultation with the Medical Monitor.

**CONFIDENTIAL**219239  
Protocol

Participants must be monitored weekly until uACR or eGFR resolve, stabilize, or return to within baseline values.

If acute glomerulonephritis is confirmed or probable [i.e., meets clinical definition of RPGN if biopsy not feasible], delay in treatment of suspected RPGN should be avoided.

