#### **7.1.4. Drug induced vascular injury and complement activation**

If the participant develops signs/symptoms of potential complement activation/DIVI including (but not limited to) new onset: persistent joint pain not resolved with simple analgesia, peripheral neuropathy, vasculitis/purpuric rash, signs of renal involvement, for example (haematuria; increasing presence of blood on urine microscopy, increasing urine ACR, rising creatinine, falling GFR), jaundice, haemolysis and/or thrombocytopenia, in addition to relevant investigations based on the participant's symptoms and signs, the following tests should also be conducted: C3, C4, Factor Bb, C5a, Rheumatoid factor, cryoglobulins (locally if available), ANCA, SPEP, UPEP, hs-CRP and compared to baseline values, if available.

Additional complement analyses for example CH50, Factor Bb level, Factor H level, sC5b-9 and samples for MCP-1 should also be considered in discussion with the Medical Monitor (who may consult with the internal Safety Panels).

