### **8.3.5. Clinical safety laboratory tests**

- See Section [10.2](#) for the list of clinical laboratory tests to be performed in accordance with lab manual and the SoA (Section [1.3](#)).
- The investigator must review the laboratory report, document this review, and record any clinically significant changes occurring during the study as an AE. The laboratory reports must be filed with the source documents. Clinically significant

**CONFIDENTIAL**219239  
Protocol

abnormal laboratory findings are those judged at investigator discretion based on being more severe than expected for the participant's condition.

- All laboratory tests with values considered clinically significantly abnormal during participation in the study should be repeated until the values return to normal or baseline or are no longer considered clinically significantly abnormal by the investigator or Medical Monitor.
  - If such values do not return to normal/baseline within a period of time judged reasonable by the investigator, the aetiology should be identified and the Sponsor notified.
  - If laboratory values from non-protocol specified laboratory tests performed at the institution's local laboratory require a change in participant management or are considered clinically significant by the investigator (e.g., SAE or AE or dose modification), then the results must be recorded.

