#### **8.4.4.4. Renal Injury**

Glomerulonephritis, including rapidly progressing glomerulonephritis, has been reported with ASOs and is thought to be a result of the proinflammatory effect of ASOs. Accumulation of antisense oligonucleotides in proximal tubule cells of the kidney, is thought to sometimes lead to increased tubular proteinuria (as described in preclinical studies). Increases in urine protein have been described in the clinic.

A monitoring strategy of renal function (e.g., serum creatinine, ACR) is presented in Section [7.1.3](#)

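### Section 7.1.3 asks for renal findings to be confirmed with a new blood sample, but two of its three triggers are urine measures that blood cannot confirm

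*Protocol*

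**What the plan says.** Protocol Section 7.1.3 (renal monitoring) opens with one instruction that applies to every trigger: "results should be confirmed (with a new blood sample), and if confirmed, further evaluation for alternative causes should be pursued". The Medical Monitor is to be consulted. Three triggers follow: a persistent uACR above 0.3 mg/mg; more than 5 "red blood cells per high power field confirmed by urine microscopy", unless there is a known cause; and a gradual, consistent fall in eGFR from baseline.

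The work-up comes next and depends on that step: "Following confirmation of the criteria above, if underlying cause other than drug-induced renal injury is not confirmed", further evaluation may include, among other tests, a 24-hour urine analysis, urine microscopy, and serum urea and creatinine. A separate paragraph then says: "Participants must be monitored weekly until uACR or eGFR resolve, stabilize, or return to within baseline values".

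Section 8.4.4.4 lists renal injury as an adverse event of special interest and refers back: "A monitoring strategy of renal function (e.g., serum creatinine, ACR) is presented in Section" 7.1.3. The SAP (4.5.1.1 and 4.5.2.3) also treats renal injury as an event of special interest. It summarises the renal monitoring events recorded in the eCRF and cites 7.1.3 for the criteria.

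**The concern.** A confirmation step should repeat the measurement that was abnormal. For uACR and urinary red cells, the specimen named in 7.1.3 does not contain the quantity in question. Followed literally, a site would draw blood, learn nothing about whether the albuminuria or haematuria was real, and still need confirmation before moving to further evaluation.

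What is at stake is the clarity of a safety rule for an event of special interest, in healthy volunteers who gain no direct benefit from the study. The pharmacokinetic endpoints are not involved.

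**Working it through.** No sample size, power or error rate is involved, and the plan gives no figure to reproduce. The check sets the triggers against the named specimen, then asks whether any other text supplies the right one.

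**Step 1. Triggers by specimen**

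| Trigger in 7.1.3 | Specimen it is measured in | Can a new blood sample confirm it? |
|---|---|---|
| Persistent uACR above 0.3 mg/mg | Urine (Table 11 lists ACR as a urine test) | No |
| More than 5 red cells per high-power field | Urine (the trigger itself specifies urine microscopy) | No |
| Gradual, consistent fall in eGFR | Blood | Yes |

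Not confirmable from blood: 2/3 = 67%. Confirmable from blood: 1/3 = 33%. This counts rules. It does not say how often either urine trigger will occur.

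**Step 2. Is the confirmation step operative?** Yes. Further evaluation is conditional on confirmation in the lead-in, and the work-up paragraph repeats the condition. The urine tests in the work-up list come after that condition, so they are not offered as the confirming test.

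**Step 3. Does other text supply a urine repeat, and does it correct the specimen?**

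- *The word persistent in the uACR trigger.* It implies more than one urine result, but gives no number or interval. It is part of the trigger, and the lead-in applies once the trigger is observed.
- *Urine microscopy in the red cell trigger.* This is the right specimen, but again part of the trigger. Table 11 makes microscopy follow an abnormal blood or protein result and does not ask for a new urine sample.
- *Weekly monitoring in 7.1.3.* Following uACR weekly needs urine, and the sentence is not worded as conditional on confirmation. It names uACR and eGFR but not red cells, and it does not change the confirmation instruction.
- *Schedule of Activities, Table 2, footnote 4.* Out-of-range Day 15 results for chemistry, haematology and urinalysis are repeated on Day 29 and, if still out of range, on Day 43. This is a real urinalysis repeat. Urine ACR has its own row without that footnote.
- *Section 8.3.5.* Clinically significantly abnormal tests "should be repeated until the values return to normal or baseline" or are no longer considered clinically significant. This turns on judgement, whereas two of the 7.1.3 triggers have numerical thresholds.
- *Section 7.1.4.* Its signs of possible vascular injury include haematuria and "increasing presence of blood on urine microscopy, increasing urine ACR, rising creatinine, falling GFR", and it leads to a work-up with no confirmation step. It is a parallel route and does not confirm a 7.1.3 trigger.

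Each of these limits the practical effect. None names a repeat urine sample as the 7.1.3 confirmation.

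**Step 4. The neighbouring section.** Section 7.1.2 also asks for a new blood sample, to re-check platelet counts. Blood is correct there. The phrase may have been carried over into 7.1.3, but the documents do not show this.

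**The case against.** The best case against the point is that it is a slip of wording with no demonstrated consequence. Urine is already collected again through the routes in the working. Section 8 also allows unscheduled samples for safety reasons, and Appendix 2 allows additional tests at any time. This is a single-dose study, so no dosing decision waits on confirmation, and further evaluation is discretionary and agreed with the Medical Monitor. A competent site would repeat the urine test anyway. The 67% is two bullets out of three, not an effect size. Finally, putting urine in place of blood could lose a creatinine value just when albuminuria or haematuria appears.

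Most of this stands as a limit on importance: no delay, harm or data effect has been shown, and the 67% should be read only as a count. It does not rescue the instruction. None of these provisions changes the specimen named in the confirmation sentence, and Section 8 makes adherence essential and allows no waivers, so the plan should not rely on sites departing from its wording.

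The lost blood draw is a weak objection. Clinical chemistry, which includes creatinine, shares a Schedule of Activities row with urinalysis, and serum creatinine stays in the 7.1.3 work-up list. The fix can also keep a creatinine sample explicitly.

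**Conclusion.** The point holds. The confirmation specimen in 7.1.3 is right for one of three renal triggers and cannot work as written for the other two. It should be corrected because it sits in the monitoring rule for an event of special interest, but its practical impact is low. There is no effect on Cmax, AUC(0-inf) or the planned analyses.

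The conclusion rests on the plain wording of 7.1.3 and on one assumption, that eGFR is derived from a blood measure. The protocol gives no eGFR formula, but Table 11 lists creatinine under clinical chemistry.

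**What to change.** In Section 7.1.3, replace the parenthetical with a repeat of the same specimen: a new urine sample for uACR and urinary red cells, and a new blood sample for creatinine and eGFR. If the sponsor wants renal function checked whenever a urine trigger appears, add that serum creatinine is taken alongside the repeat urine sample.

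The cost is one phrase in the protocol. For the two urine triggers, a urine sample takes the place of a blood draw that cannot answer the question, or accompanies it if the optional creatinine is kept. No new assay or scheduled visit is needed, and the SAP does not change.

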#### **7.1.4. Drug induced vascular injury and complement activation**

If the participant develops signs/symptoms of potential complement activation/DIVI including (but not limited to) new onset: persistent joint pain not resolved with simple analgesia, peripheral neuropathy, vasculitis/purpuric rash, signs of renal involvement, for example (haematuria; increasing presence of blood on urine microscopy, increasing urine ACR, rising creatinine, falling GFR), jaundice, haemolysis and/or thrombocytopenia, in addition to relevant investigations based on the participant's symptoms and signs, the following tests should also be conducted: C3, C4, Factor Bb, C5a, Rheumatoid factor, cryoglobulins (locally if available), ANCA, SPEP, UPEP, hs-CRP and compared to baseline values, if available.

Additional complement analyses for example CH50, Factor Bb level, Factor H level, sC5b-9 and samples for MCP-1 should also be considered in discussion with the Medical Monitor (who may consult with the internal Safety Panels).

### **7.2. Participant discontinuation/withdrawal from the study**

A participant may withdraw from the study at any time at the participant's own request for any reason (or without providing any reason).

A participant may be withdrawn at any time at the discretion of the investigator for safety, behavioral, or compliance reasons.

Investigators will attempt to contact participants who do not return for scheduled visits or follow-up.

At the time of discontinuing from the study, if possible, an early withdrawal visit should be conducted, as shown in the SoA. See SoA for data to be collected at the time of study discontinuation and follow-up and for any further evaluations that need to be completed.

The participant will be permanently discontinued from the study at that time.

All data and samples collected up to and including the date of withdrawal of/last contact with the participant will be included in the study analyses. If the participant withdraws consent for disclosure of future information, the sponsor may retain and continue to use any data collected before such a withdrawal of consent.

If a participant withdraws from the study, the participant may request destruction of any samples taken and not tested, and the investigator must document this in the site study records.

**CONFIDENTIAL**219239  
Protocol

The primary reason for participant discontinuation/ withdrawal from the study will be documented in the CRF/eCRF for reasons including, but not limited to the list below:

Reasons	Additional items/Sub-reasons
Lost to follow-up	Subject Relocated Subject was Incarcerated Other, specify
Physician Decision	Specify
Protocol Deviation	Specify
Site Terminated by Sponsor	Specify
Withdrawal by Participant	Burden of Procedure Participant Relocated Other
Death	Specify

Participants who are withdrawn from the study because of AEs/SAEs must be clearly distinguished from participants who are withdrawn for other reasons. Investigator will follow participants who are withdrawn from the study due to an AE/SAE as per instructions in Section 10.3.4.5.

### 7.3. **Lost to follow-up**

A participant will be considered lost to follow-up if the participant repeatedly fails to return for scheduled visits and is unable to be contacted by the study site.

The following actions must be taken if a participant fails to return to the clinic for a required study visit:

- The site must attempt to contact the participant and reschedule the missed visit as soon as possible, counsel the participant on the importance of maintaining the assigned visit schedule and ascertain whether the participant wishes to and/or should continue in the study.
- Before a participant is deemed lost to follow-up, the investigator or designee must make every effort to regain contact with the participant where possible, 3 telephone calls, and if necessary, a certified letter to the participant's last known mailing address or local equivalent methods. These contact attempts should be documented in the participant's medical record.
- Should the participant continue to be unreachable, the participant will be considered to have withdrawn from the study.

## 8. **STUDY ASSESSMENTS AND PROCEDURES**

- Study procedures and their timing are summarized in the SoA (Section 1.3). Protocol waivers or exemptions are not allowed.
- Adherence to the study design requirements, including those specified in the SoA, is essential and required for study conduct.

**CONFIDENTIAL**219239  
Protocol

- All screening evaluations must be completed and reviewed to confirm that potential participants meet all eligibility criteria. Subjects who have signed informed consent but are not eligible to proceed should be recorded in the eCRF with a status of 'screen failure'.
- The maximum amount of blood collected from each participant over the duration of the study, including any extra assessments that may be required, will not exceed 500 mL.
- Repeat or unscheduled samples may be taken for safety reasons or for technical issues with the samples.

## **8.1. Administrative procedures**

### **8.1.1. Collection of demographic data**

Record demographic data such as date of birth, sex, race, and ethnicity in the participant's eCRF.

Collection of sex, race and ethnicity data is necessary to assess and monitor the diversity of the trial participants, and to determine if the trial participants are truly representative of the impacted population.

### **8.1.2. Medical history**

The participant's medical history will be obtained by interviewing the participant and/or review of the participant's medical records. Any pre-existing conditions, signs and/or symptoms present prior to study start will be recorded in the eCRF.

## **8.2. Efficacy assessments**

Not applicable for this study.

## **8.3. Safety assessments**

Planned timepoints for all safety assessments are provided in the SoA (Section 1.3). Additional time points for safety tests (such as vital signs, physical examinations, and laboratory safety tests) may be added during the course of the study based on newly available data to ensure appropriate safety monitoring.

### **8.3.1. Physical examination/history directed physical examination**

- At screening, a complete physical examination will include, at a minimum, assessments of the skin, cardiovascular, respiratory, gastrointestinal, and neurological systems. Height and weight will also be measured and recorded.
- Symptoms directed examination will be conducted at all other time points.

**CONFIDENTIAL**219239  
Protocol

- Investigators should pay special attention to clinical signs related to previous serious illnesses.

### **8.3.2. Injection site reactions**

- Injection site reactions are any experiences which occur at the site of injection of the study treatment. Participants will be monitored closely for ISRs and ISRs should be recorded as AEs on a specific ISR eCRF page.
- Injection site reactions will be graded according to the criteria provided in the DAIDS grading table (see [Appendix 7](#)).

### **8.3.3. Vital signs**

- Temperature, heart rate, respiratory rate, and blood pressure will be assessed as outlined in the SoA (Section [1.3](#)).
- Blood pressure and heart rate measurements should be assessed in semi supine position (preferred, but not required) with a completely automated device. Manual techniques will be used only if an automated device is not available.
- Blood pressure and heart rate measurements should be preceded by at least 5 minutes of rest for the participant in a quiet setting without distractions (e.g., television, cell phones)
- For triplicate blood pressure and heart rate measurements before dosing, 3 consecutive readings will be recorded at intervals of at least 1 minute. The full set of triplicates should be completed within a 5-minute recording period. The average of the 3 readings will be recorded.
- Vital signs should be taken before blood collection for laboratory tests.

### **8.3.4. Electrocardiograms**

- 12-lead ECGs will be obtained as outlined in the SoA (Section [1.3](#)), using an ECG machine that automatically calculates the heart rate and measures PR, QRS, QT, and QTc intervals. Manual calculation, if an automatic calculation is not available, is acceptable.
- For triplicate measurements before dosing, 3 consecutive readings will be recorded at intervals of at least 1 minute. The full set of triplicates should be completed within a 5 minute recording period. The average of the 3 readings will be recorded.
- ECGs should be taken before blood collection for laboratory tests.

### **8.3.5. Clinical safety laboratory tests**

- See Section [10.2](#) for the list of clinical laboratory tests to be performed in accordance with lab manual and the SoA (Section [1.3](#)).
- The investigator must review the laboratory report, document this review, and record any clinically significant changes occurring during the study as an AE. The laboratory reports must be filed with the source documents. Clinically significant

**CONFIDENTIAL**219239  
Protocol

abnormal laboratory findings are those judged at investigator discretion based on being more severe than expected for the participant's condition.

- All laboratory tests with values considered clinically significantly abnormal during participation in the study should be repeated until the values return to normal or baseline or are no longer considered clinically significantly abnormal by the investigator or Medical Monitor.
  - If such values do not return to normal/baseline within a period of time judged reasonable by the investigator, the aetiology should be identified and the Sponsor notified.
  - If laboratory values from non-protocol specified laboratory tests performed at the institution's local laboratory require a change in participant management or are considered clinically significant by the investigator (e.g., SAE or AE or dose modification), then the results must be recorded.

### **8.3.6. Pregnancy testing**

- Female participants of childbearing potential must perform a screening serum pregnancy test, and a serum or urine pregnancy test on admission to the clinical unit, before the administration of any dose of study intervention. Pregnancy testing must be done even if the participant is menstruating at the time of the study visit. The study intervention may only be administered if the pregnancy test is negative.
- Refer to Section [8.4.6](#) for the information on study continuation for participants who become pregnant during the study.

## **8.4. Adverse Events (AEs) serious adverse events (SAEs), and other safety reporting**

The definitions of AEs or SAEs can be found in Section [10.3 \(Appendix 3\)](#).

AEs will be reported by the participant.

The investigator and any qualified designees are responsible for detecting, documenting, and recording events that meet the definition of an AE or SAE and remain responsible for following up AEs that are serious, considered related to the study intervention or the study, or that caused the participant to discontinue study intervention (see Section [7](#)).

The method of recording, evaluating, and assessing causality of AEs and SAEs and the procedures for completing and transmitting SAE reports are provided in Section [10.3 \(Appendix 3\)](#).

